#### **1.4.3            *Phase 1/2 Study in CKD Patients on Hemodialysis (COR-001-01)***

This study was a Phase 1/2 Randomized, Double-Blind, Placebo-Controlled, Cohort Dose-Escalation Study in Hemodialysis Patients to Assess the Safety, Pharmacokinetics, and Pharmacodynamics of Multiple IV Doses of Ziltivekimab. The target population was composed of hemodialysis patients who had a predefined genetic makeup, and who displayed high serum IL-6 levels and high ESA requirements.

After IV administration, COR-001 concentrations increased in a dose-related manner and appeared to decline in a biphasic manner. The terminal half-life of Ziltivekimab ranged from 38 to 44 days and there was no evidence of body weight as a covariate. Exposure levels were unaffected by hemodialysis and there was no pattern of altered PK to suggest neutralizing antibodies. Further details of this study may be found in the IB.

**Figure 4** Ziltivekimab causes Dose-Dependent Decreases in hs-CRP from Baseline in ESRD Patients

Abbreviations: hs-CRP = high-sensitivity C-reactive protein; N = number of subjects

Note: Ziltivekimab (2 mg, 6 mg or 20 mg IV) Q2 weeks; Data from Pharmacodynamic Analysis Population.

Note: After checking the data normality, the parameter was shown as Median (Q1/Q3).

Source: Protocol No: COR-001-01 Final Analysis

There was a greater incidence of Treatment Emergent Adverse Events (TEAE) in each of the Ziltivekimab groups than in the placebo group, there was not a clear dose response. The 6 mg COR-001 dose group had the greatest incidence of patients with at least one TEAE, and the two TEAEs that occurred at the highest incidence in the trial were reported in this treatment group (congestive cardiac failure and dyspnea which each occurred in 4 patients).

Serious adverse events (SAEs) occurred at a higher rate in the 6 and 20 mg dose groups than in the placebo and 2 mg groups. The 6 mg group had the greatest incidence of SAEs (7 patients reporting a total 14 SAEs), and all 4 of the congestive cardiac failure events in the 6 mg group were considered serious. None of the SAEs in any group were assessed as treatment related. There were 4 patients who had SAEs with a fatal outcome; sepsis (Patient [REDACTED]) and sudden cardiac death (Patient [REDACTED]) in the 6 mg group and sepsis ([REDACTED]) and cardiac arrest ([REDACTED]) in the 20 mg group. None of the deaths were attributed to study drug; more information on the Safety results from study COR-001-01 can be found in the Investigator Brochure.

#### **1.4.4            *Conclusions on Ziltivekimab Treatment of Anemia in CKD***

Ziltivekimab is a potent and highly selective fully-human anti-IL-6 antibody in development for the treatment of anemia in CKD patients. Ziltivekimab has shown marked reductions in hs-CRP levels (inflammation) within the first weeks of administration and continuing throughout the treatment period. In summary, the clinical evidence presented here supports investigating Ziltivekimab as a product to reduce hs-CRP based inflammation and an ultimate reduction in anemia-associated CVD in the proposed patient population.

## **2 STUDY GOAL AND OBJECTIVES**

Patients with NDD-CKD, who have evidence of systemic inflammation with increased cardiovascular risk, will be enrolled into this trial. The purpose of this trial is to determine a dose to select for a potential cardiovascular outcome trial with Ziltivekimab. The current trial will determine which dose of Ziltivekimab will have a significant reduction in hs-CRP with acceptable increases in LDL-C or triglycerides and without clinically meaningful reductions in neutrophils and platelet counts. Doses to be tested will be 7.5 mg, 15 mg and 30 mg subcutaneous monthly compared to placebo for six months.

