### **2.4 Safety objectives:**

To evaluate the safety of three dose levels of Ziltivekimab compared to placebo.

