#### ***11.4.3 Efficacy Analysis***

For all efficacy variables, the number of patients (n), mean, standard deviation (SD), median, quartiles (Q1 and Q3), minimum (min) and maximum (max) values for the observed value, change from baseline, or percent change from baseline (as applicable) will be reported. The difference (Ziltivekimab - Placebo) in changes or percent changes (as applicable) will be presented.

A mixed model for repeated measures (MMRM) will be used to evaluate change or percent change from baseline. The model will include variables for baseline hemoglobin ( $\geq 11$  or  $< 11$  g/dL), CKD Stage (3, 4 or 5), treatment group, visit and treatment group-by-visit interaction as categorical fixed effects, baseline value and baseline-by-visit interaction will be included as covariates. The least squares means for each dose, the least squares mean differences from placebo along with the associated 95% confidence intervals (CIs) and p-values will be presented. If the normality assumption is not met, a nonparametric test will be selected for efficacy analysis. Details of normality test and nonparametric test will be provided in the Statistical Analysis Plan.

An unstructured covariance matrix will be used to model the within-subject correlation. The Kenward-Roger approximation will be used to adjust the denominator degrees of freedom. The analysis will be performed based on all observed post-baseline scores without any imputation of missing data. In the case when the MMRM fails to converge using an unstructured covariance matrix in any stage, a less stringent covariance matrix (e.g., autoregressive 1) will be used.

Sensitivity analyses will be conducted to explore the robustness of the result for primary efficacy endpoint based on MMRM. Full details will be pre-specified in SAP and documented prior to database lock of the study.

The differences in proportions and 95% CIs will be based on the normal approximation to binomials.

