#### 11.4.4.3 Exploratory

- Difference in percent change in hs-CRP levels from Baseline to End of Treatment (Weeks 23 through 24) between each active group and placebo.
- Difference in percent change in serum NT-pro-BNP from Baseline (average of the NT-pro-BNP value prior to randomization and Day 1) to Week 13 and to End of Treatment (Weeks 23 through 24) between each active group and placebo.
- Difference in change in SAA from Baseline to End of Treatment (Weeks 23 through 24) between each active group and placebo.
- Difference in percent change in fibrinogen from Baseline to End of Treatment (Week 24) between each active group and placebo.
- Difference in change in hemoglobin from Baseline (average of the two most recent hemoglobin values prior to randomization and Day 1) to Week 13 and to End of Treatment (Weeks 23 through 24) between each active group and placebo.
- Difference in change in serum albumin from Baseline (average of the two most recent serum albumin values prior to randomization and Day 1) to Week 13 and to End of Treatment (Weeks 23 through 24) between each active group and placebo.
- Proportion of patients achieving hs-CRP response at Week 13 and to End of Treatment (Weeks 23 through 24), defined as hs-CRP <2.0 mg/L in each active group and placebo.
- Difference in change in ST2 from Baseline to Week 13 and to End of Treatment (Week 24) between each active group and placebo.
- Difference in percent change in Lp(a) from Baseline to Week 13 and to End of Treatment (Weeks 23 through 24) between each active group and placebo.

- Difference in percent change in LDL-C, triglycerides, ApoB, ApoA1, ApoB/ApoA1, and lipid profile by NMR spectroscopy from Baseline to Week 13 and to End of Treatment (Weeks 23 through 24) between each active group and placebo.
- Difference in change of creatinine based eGFR and cystatin C-based eGFR from Baseline to Week 13 and to the End of Treatment (Weeks 23 through 24) between each active group and placebo.
- Difference in change of UACR from Baseline to Week 13 and to End of Treatment (Weeks 23 through 24) between each active group and placebo.
- Difference in change of the total fatigue score (PROMIS Fatigue 13a short form and selected items from the PROMIS Fatigue item bank) from Baseline to Week 13 and to End of Treatment (Weeks 23 through 24) between each active group and placebo.

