#### **11.4.5       Safety Analysis**

##### **11.4.5.1    Adverse Events**

The adverse event verbatim descriptions (investigator terms from the CRF) will be classified into medical terminology using the Medical Dictionary for Regulatory Activities (MedDRA). Adverse events will be coded to primary System Organ Class (SOC) and preferred term (PT) using MedDRA, Version 21.0.

Treatment emergent adverse events (TEAEs) are defined as AEs that initiated or worsened on or after the date of first dose of study drug up to the end of safety-follow-up. For AEs occurring on the first dosing day, if the start time cannot be ascertained, the event will be counted as treatment-emergent.

Safety events of special interest (Section 9.3) will be summarized by dose group and treatment assignment.

An overview of AEs will be provided including counts and percentages of subjects with the following:

- Any TEAEs (overall and by maximum severity)
- Any study drug related TEAEs (overall and by maximum severity)
- Any TEAEs of special interest (overall and by maximum severity)
- Any serious AEs (SAEs)
- Any treatment-emergent serious AEs (TESAEs)
- Any TEAEs leading to discontinuation of study drug
- Any TEAEs leading to discontinuation of study
- Any AEs leading to death
- Any severe hematologic AEs (see [Section 11.4.5.7](#))
- Any severe non-hematologic AEs

The number and percentage of patients reporting TEAEs and SAEs for each preferred term will be tabulated by system-organ class, by system- organ class and severity, and by system-organ class and relationship to Study Drug. If more than one event occurred with the same preferred term for the same patient, the patient will be counted only once for that preferred term using the most severe or related occurrence for the summary by severity, or relationship to study drug, respectively.

Listings will be presented specifically for SAEs and TEAEs leading to discontinuation of study drug.

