#### 11.4.5.2    Laboratory Tests

Laboratory values (excluding efficacy laboratory parameters) will be summarized by treatment group, including changes from baseline at each visit.

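### Neutrophil and platelet reductions are criteria for choosing the dose, but the protocol gives them no estimated difference from placebo and no confidence interval

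*Protocol*

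**What the plan says.** Section 2 gives the aim: "The purpose of this trial is to determine a dose to select for a potential cardiovascular outcome trial with Ziltivekimab". It then says the trial will determine which dose reduces hs-CRP significantly with "acceptable increases in LDL-C or triglycerides and without clinically meaningful reductions in neutrophils and platelet counts". Section 2.4 states the safety objective: "To evaluate the safety of three dose levels of Ziltivekimab compared to placebo".

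The four harm variables named in Section 2 are handled in two ways.

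- **LDL-C and triglycerides** are exploratory efficacy variables. Section 11.4.4.3 lists "Difference in percent change in LDL-C, triglycerides, ApoB, ApoA1, ApoB/ApoA1, and lipid profile by NMR spectroscopy from Baseline to Week 13", and also to End of Treatment, for each active group against placebo. Section 11.4.3 analyses change or percent change by MMRM and says that "the least squares mean differences from placebo along with the associated 95% confidence intervals (CIs) and p-values will be presented".
- **Neutrophils and platelets** are in no efficacy list. They fall under Section 11.4.5.2: "Laboratory values (excluding efficacy laboratory parameters) will be summarized by treatment group, including changes from baseline at each visit". Severe cytopenias are also special-interest events (Sections 3.1.2 and 9.3), and for these Section 11.4.5.1 says: "Safety events of special interest (Section 9.3) will be summarized by dose group and treatment assignment".

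**The concern.** A criterion that a dose is free of a meaningful reduction is a statement about absence. It can be supported only by showing what size of reduction the data exclude. For the lipids, the protocol supplies the quantity needed, an estimated difference from placebo with its interval. For the two blood counts it supplies a table of values and changes per arm and stops there.

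At stake is how the blood-count part of the dose choice can be read. Without an interval, a small observed difference or an empty row of severe events shows what was seen in about 60 patients. It does not show what remains possible. The issue is live for this drug class: Section 3.7 notes that anti-IL-6 therapies lower neutrophil counts and may cause frank neutropenia.

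**Working it through.** **1. The protocol's own figure.** Section 11.1 assumes a difference of 60.74 percentage points in hs-CRP, SD 16.893, 54 evaluable per group and two-sided alpha 0.05.

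- Standardised difference: 60.74 / 16.893 = 3.60.
- Power ≈ Φ(3.60 × √(54/2) − 1.96) = Φ(18.7 − 1.96) ≈ 1.00, in agreement with the stated figure of more than 99%.
- Dropout of 10%: 54 / 0.9 = 60 per group, as stated.

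The sample size therefore reproduces, but it rests on hs-CRP alone. Section 11.1 gives no SD, rate or precision for neutrophils or platelets.

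**2. Precision for a mean difference in counts.** No SD is given, so the result is in units of the SD of the change analysed. For two groups of n patients the 95% half-width is 1.96 × √(2/n) SD.

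| n per group | Normal quantile | t quantile |
|---|---|---|
| 54 | 1.96 × √(2/54) = 0.377 SD | 0.382 SD |
| 60 | 1.96 × √(2/60) = 0.358 SD | 0.362 SD |

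An observed difference of exactly zero would thus still be compatible with a true mean fall of about 0.36 to 0.38 SD. This is a plain two-group calculation. Baseline adjustment in the MMRM may narrow the interval if the SD is that of the unadjusted change.

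**3. Precision for threshold events.** With 0 events in n patients, the exact two-sided 95% upper limit is 1 − 0.025^(1/n).

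- n = 60: 1 − 0.025^(1/60) = 6.0%.
- n = 54: 1 − 0.025^(1/54) = 6.6%.

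The chance of seeing no event among 60 when the true rate is r is (1 − r)^60. The rates below are assumptions, because the protocol gives none.

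| Assumed true rate | Chance of 0 in 60 |
|---|---|
| 1% | 55% |
| 2% | 30% |
| 3% | 16% |
| 5% | 5% |

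**4. Why exact intervals.** The normal approximation that Section 11.4.3 names for proportions has standard error √(p(1 − p)/n). At p = 0 this is zero, so the interval has no width in the very case that matters most here.

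**5. What individual-level capture adds.** Special-interest reporting covers neutrophils below 500/mm³, or below 1000/mm³ with infection, and platelets below 50,000/mm³, or below 75,000/mm³ with TIMI major bleeding. Section 4.5 lists neutrophils below 1000/mm³ or platelets below 50,000/mm³ alone, on two assessments, as grounds for withholding drug. Section 9.1 makes an abnormality that interrupts treatment a ground for recording an adverse event. Confirmed severe cytopenias should therefore reach the by-group tables. All of these rules apply to single patients. None yields a mean difference between a dose and placebo, or an interval for an event rate.

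**The case against.** The strongest case against the point has five parts.

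- **Detail belongs in the SAP.** Section 11 refers there for all planned analyses, and nothing in Section 11.4.5.2 forbids differences or intervals. This stands as a caution, since the SAP is not at hand. But the protocol itself states the dose criterion and itself fixes the summary method for these counts, and the two do not match.
- **Placebo is shown.** A reader might infer that these counts are not compared with placebo at all. The documents do not support that. The by-group tables put placebo beside each dose with n, mean and SD (Section 11.3.1), and an unadjusted interval could be worked out from them. What is absent is a prescribed estimate with its interval.
- **No rule equates silence with safety.** A reader might infer that a p-value above 0.05, or zero events, will count as meeting the criterion. No section says so. For the same reason, type II error rates of a two-sample test are not evidence here, because no such test is planned for these counts.
- **Judgement is legitimate in Phase 2.** Weighing estimates without a formal margin is a defensible choice in a dose-selection trial. This stands, and it is why no margin is asked for.
- **Harm need not decide the dose.** A reader might infer from the high hs-CRP power that blood counts alone will separate the doses. That power is for each dose against placebo, not between doses. The size of the hs-CRP fall, the proportion below 2.0 mg/L and the PK-PD analysis can also inform the choice.

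**Conclusion.** The point holds as a mismatch inside the protocol. Two of the four harm variables that Section 2 ties to the dose choice, neutrophils and platelets, have no prescribed difference from placebo and no confidence interval. The other two, LDL-C and triglycerides, have both.

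On the planned group sizes, what the prescribed tables leave unstated is a mean difference of about 0.36 to 0.38 SD either side of the estimate, and an event rate of up to 6.0% after 0 of 60. These figures depend only on 54 to 60 patients per group and standard formulas. They do not show that a fall of 0.38 SD or a rate of 6.0% is clinically meaningful. The protocol gives no SD, no event rate and no definition of a meaningful reduction, so no claim is made that a relevant harm would be missed. This is an improvement worth making, and it does not put the primary result in doubt.

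**What to change.** Three changes, best made before the Week 13 unblinding described in Section 12.2:

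1. In Section 11.4.5.2, analyse change from baseline in neutrophil count and platelet count with the Section 11.4.3 MMRM. Report the least squares mean difference of each dose from placebo with its 95% confidence interval at Week 13 and at Weeks 23 to 24.
2. In the same section, tabulate by arm the patients with any post-baseline value below the count thresholds the protocol already uses (neutrophils 1000 and 500/mm³; platelets 75,000 and 50,000/mm³). Give exact 95% confidence intervals, and count patients regardless of concurrent infection or bleeding.
3. In Section 2, state that the dose choice is informed by these intervals, and that non-significance or zero events alone is not taken as absence of a reduction.

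No formal non-inferiority margin is required, and no new clinical threshold is proposed. Hematology is already scheduled throughout treatment and follow-up (Sections 5.3 and 5.4), so no patients, visits or samples are added. The cost is some wording and a few tables. The sponsor may also have to report that a reduction of a given size could not be excluded for a dose.

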### **2.1 Primary objective:**

To evaluate the effects of Ziltivekimab compared to placebo on markers of inflammation (i.e. hs-CRP).

### **2.2 Secondary objectives:**

To evaluate the effects of Ziltivekimab compared to placebo on markers of inflammation and cardiovascular risk: serum amyloid A (SAA) and fibrinogen.

### **2.3 Pharmacokinetic objectives:**

To evaluate the pharmacokinetics (PK) and PK-Pharmacodynamic (PK-PD) modeling of Ziltivekimab following multiple doses at three different levels.

### **2.4 Safety objectives:**

To evaluate the safety of three dose levels of Ziltivekimab compared to placebo.

### **2.5 Exploratory objectives:**

To evaluate the effects of Ziltivekimab compared to placebo on markers of anemia (hemoglobin).

To evaluate the effects of Ziltivekimab compared to placebo on markers of inflammation-malnutrition (i.e. albumin).

To evaluate the effects of Ziltivekimab compared to placebo on markers of cardiovascular risk (i.e. N-terminal prohormone-B-type natriuretic peptide [NT-pro-BNP]).

To evaluate the effects of Ziltivekimab compared to placebo on additional markers of cardiovascular risk (suppression of tumorigenicity 2 [ST2]).

To evaluate the effects of Ziltivekimab compared to placebo on markers of atherosclerosis risk: LDL-C, triglycerides, ApoB, ApoA1, ApoB/ApoA1, lipid profile by nuclear magnetic resonance (NMR) spectroscopy, and Lp(a).

To evaluate the effects of Ziltivekimab compared to placebo on markers of kidney function, (i.e. cystatin C, estimated GFR) and kidney damage, (i.e. urine albumin-to-creatinine ratio [UACR]).

To determine Ziltivekimab trough drug levels following multiple Ziltivekimab doses at three different dose levels.

To evaluate the effects of three dose levels of Ziltivekimab compared to placebo on patient reported outcomes (PRO): Patient-Reported Outcomes Measurement Information System (PROMIS®) Fatigue 13a short form, selected items from the PROMIS fatigue item bank, the Optum SF-36 v2® Health Survey, a Corvidia PRO, the PROMIS interest in sexual activity item, the patient global impression of change (PGIC), patient global impression of severity (PGIS), and the EQ-5D-5L.

To evaluate the psychometric properties of the PROMIS Fatigue 13a short form and selected items from the PROMIS fatigue item bank, and the Corvidia electronic PRO (ePRO) items in CKD patients.

To evaluate the effects of Ziltivekimab on systemic iron availability: transferrin saturation (TSAT), reticulocyte hemoglobin content (CHr) and total iron binding capacity (TIBC), systemic iron stores (serum ferritin), serum iron and systemic iron regulation (serum hepcidin).

To evaluate the effects of Ziltivekimab compared to placebo on markers of cardiovascular risk (i.e. NT-pro-BNP) in patients with baseline NT-pro-BNP > 250 pg/mL.

To evaluate the effects of Ziltivekimab compared to placebo on markers of anemia in patients with baseline hemoglobin < 11 g/dL.

To evaluate the effects of Ziltivekimab compared to placebo on markers of inflammation-malnutrition (i.e. albumin) in patients with baseline albumin < 4.0 g/dL.

### 3 INVESTIGATIONAL PLAN

#### 3.1 Overall Study Design and Plan: Description

This is a randomized, double-blind, placebo-controlled trial designed to evaluate the efficacy, safety, and pharmacokinetics of Ziltivekimab at three dose levels (7.5 mg, 15 mg or 30 mg) compared to placebo in patients with stage 3-5 CKD, not on dialysis, who have evidence of inflammation with high cardiovascular risk.

Patients will undergo a Screening Period of up to 14-days during which inclusion and exclusion criteria will be evaluated. Patients who meet all inclusion criteria and no exclusion criteria will be randomized to one of three Ziltivekimab dose levels (7.5 mg, 15 mg or 30 mg) or placebo for a 24-week Treatment Period. Patient randomization will be stratified by baseline hemoglobin ( $\geq 11$  or  $< 11$  g/dL) and CKD stage (3, 4 or 5).

Approximately 240 patients will be randomized 1:1:1:1 (60 per group) into the trial. All patients must meet the inclusion/exclusion criteria. After the Screening Period, randomized patients will be dosed every 28 days out to Week 21. The primary, secondary and exploratory endpoints will be analyzed at 13 weeks of dosing and then followed for additional exploratory efficacy analyses through Week 24, and then selected efficacy endpoints and safety assessments will be evaluated in the Follow-up Period Week 25 through Week 32 (Figure 5). The primary, secondary, and exploratory endpoint evaluation will take place at the end of Week 13, and the additional exploratory evaluations will take place at the End of Treatment (Weeks 23 and 24).

The patient will be randomized on Day 1 and the first dose of study drug should be administered after all assessments are conducted. Doses of study drug will be administered every 28-days for a total of 6 treatments (Weeks 1, 5, 9, 13, 17 and 21). Study visits will follow the schedule of events (Table 2).

